## Protocol Template Form

Item 1 UTHSCSA Tracking Number	HSC20150859H
--------------------------------	--------------

Item 2 Abstract / Project Summary	Provide a succinct and accurate description of the proposed research. State the purpose/aims. Describe concisely the research design and methods for achieving the stated goals. This section should be understandable to all members of the IRB, scientific and non-scientific. DO NOT EXCEED THE SPACE PROVIDED.
-----------------------------------	--

**Purpose/Objectives:** Nausea is a common symptom encountered in the Emergency Medical Services (EMS) environment that is often treated with oral or intravenous anti-emetic medications. **Research Design/Plan:** This will be a randomized equivalence study comparing the reduction in a patient's reported level of nausea after treatment with either Ondansetron or Isopropyl Alcohol

**Methods:** Patients who report nausea and/or vomiting in the normal evaluation and care of after calling 911 for Emergency Medical Care will be offered enrollment in the study. A short script will be attached to the outside of each study packet providing information about the study and its risks and benefits. Verbal or written (waiver of informed consent will be requested) permission will be obtained to start randomization. If the patient agrees to enroll then the study packet will be opened and utilized. All Advanced Life Support Ambulances in the San Antonio Fire Department will have sealed numbered opaque boxes or envelopes with either: 70% Isopropyl Alcohol swabs or ondansetron. Six Visual Nausea Severity Scoring cards will be provided with a marking pen to record timed nausea levels before and upon arrival to the Emergency Department and 15 minutes after treatment whichever comes first.

**Clinical Relevance:** This treatment has not been studied in the unique environment encountered by Paramedics in the Pre-Hospital setting. If this treatment is found to be effective, it may offer a very simple, extremely inexpensive and non-invasive (basic life support) approach for the treatment of nausea.

Item 3 Background	

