
Step-by-Step Methods:
 
RECRUITMENT AND RANDOMIZATION PROCESS Patients who report nausea and/or vomiting in the normal evaluation and care of after calling 911 for Emergency Medical Care will be offered enrollment in the study. A short script will be attached to the outside of each study packet providing information about the study. Verbal (waiver of documentation informed consent will be requested) permission will be obtained to start randomization. If the patient agrees to enroll then the study packet will be opened and utilized.
 
PROCEDURES AND LOGISTICS All Advanced Life Support Ambulances in the San Antonio Fire Department will have sealed numbered opaque boxes or envelopes with either:
 
 
• Three large 2 ply 70% Isopropyl Alcohol swabs
 
 
OR
 
 
• Ondansetron (Zofran) 4mg for IV/IM use (standard of care)
 
 
These study packets will have similar weight, shape and contour despite the contents. If needed, props may be included to make packages similar in weight, contour or sound when shaken so as to not reveal its true contents. The goal is to enroll at least 400 patients over a 1 year period.
 
For each arm, the package will contain a step by step instruction checklist. Six Visual Nausea Severity Scoring cards will be provided with a marking pen to record timed nausea levels before and upon arrival to the Emergency Department and 15 minutes after treatment whichever comes first. The treatment protocol for each arm will be:
 
70% Isopropyl Alcohol
 
 
1. Mark Time and Visual Nausea Severity Score 0-10
 
2. Remove alcohol prep with gloved hand
 
3. Place under nares of the patient
 
	
--	--

4. Instruct the patient to take three separate deep inhalations of the Isopropyl vapors through their nose
5. Record time of treatment on back of first Visual Nausea Severity Score card.
6. Mark time and Subsequent Visual Nausea Severity Scores upon arrival to the Emergency Department at indicated time intervals.
7. If patient still has significant nausea and or vomiting after ten minutes provide rescue Ondansetron therapy with 4mg of Ondansetron slow IV push or IM
8. Mark time and Visual Nausea Severity Score upon arrival to the Emergency Department on third card.
9. Document all interventions on electronic Patient Care record as per usual procedures.

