10. Complete Paramedic evaluation tool.
11. Envelope or box, with Consent, score cards and Paramedic evaluation tool will be returned to Medic Officer on duty and a new study packet will be replaced.
12. Used Study Packets will be collected by the Investigators

Ondansetron 4mg IV/IM (standard of care)

1. Mark Time and Visual Nausea Severity Score 0-10 on first enclosed card.
2. Start IV if not already done so.
3. If unable to obtain IV access in two attempts use intramuscular route.
4. Inject 4mg of Ondansetron slow IV push or IM.
5. Record time of treatment on back of first Visual Nausea Severity Score card.
6. Mark time and Second Visual Nausea Severity Score upon arrival to the Emergency Department or 10 minutes after treatment whichever comes first.
7. If patient still has significant nausea and or vomiting after ten minutes provide rescue an additional dose of Ondansetron therapy with 4mg of Ondansetron slow IV push or IM
8. Mark time and Visual Nausea Severity Score upon arrival to the Emergency Department on third card.
9. Document all interventions on electronic Patient Care record as per usual procedures.
10. Complete Paramedic evaluation tool.
11. Envelope or box, with Consent, score cards and Paramedic evaluation tool will be returned to Medic Officer on duty and a new study packet will be replaced.
12. Used Study Packets will be collected by the Investigators.

Data Analysis Plan: A secure excel spreadsheet tool will be used to abstract data from the research data collection documents and the EMS electronic patient care record. The patient will only be identified by the randomization number, incident number, age (if greater than 89 age will be indicated by <89 years), sex and date of service in the database and on all study packet materials. All relevant time intervals and Visual Nausea Severity Scores will be recorded for enrolled patients. Time to treatment will be compared between the two arms of the study as well as changes in Visual Nausea Severity Scores. Treatment failures requiring additional Ondansetron will be characterized. Paramedic will be asked to evaluate the treatment provided for ease of use, time needed to complete the treatment and their impression of effectiveness of the assigned treatment. T-test and confidence intervals will be utilized to determine statistical significance.

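### The baseline nausea score comes after the sealed packet is opened, so the baseline half of the change score can be recorded with the assignment already known

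*Combined protocol and SAP*

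**What the plan says.** Item 2 gives the design: "This will be a randomized equivalence study comparing the reduction in a" patient's reported nausea. The Data Analysis Plan in Item 6 compares changes in the nausea score between the arms, so the baseline enters every patient's outcome.

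The order of events comes from Item 6:

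- Recruitment and Randomization Process: "If the patient agrees to enroll then the study packet will be opened and utilized".
- Procedures and Logistics, on what the packet holds: "For each arm, the package will contain a step by step instruction checklist".
- Procedures and Logistics, on the cards: "Six Visual Nausea Severity Scoring cards will be provided with a marking pen". Where the cards are kept is not stated here.
- Alcohol checklist, step 1: "Mark Time and Visual Nausea Severity Score 0-10", with no card named.
- Ondansetron checklist, step 1: "Mark Time and Visual Nausea Severity Score 0-10 on first enclosed card".
- Both checklists, step 5: "Record time of treatment on back of first Visual Nausea Severity Score card".

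The packets are sealed, numbered and opaque, and are to be alike in weight, shape and contour. If needed, props may be added to "make packages similar in weight, contour or sound when shaken so as to not reveal its true contents". A short study script is fixed to the outside of each packet.

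**The concern.** Opening the packet reveals the assignment. A score that must precede treatment need not precede knowledge of the arm, and the plan secures only the former. The outcome is a subjective 0-10 rating reported by the patient. The documents do not say who marks the card, or whether the patient knows the arm at that moment. Influence could come through the way the paramedic asks for or records the score, or through the patient if the patient sees the contents.

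If such influence differs between arms and is not matched in later scores, it moves the estimated difference in reduction, and its confidence interval, by the same number of points. In an equivalence study either direction matters: a shift toward zero favours a claim of equivalence, and a shift away from zero hides it. The packets create a moment when the assignment is still concealed, but the plan does not use that moment for the one score it could protect.

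**Working it through.** **Order of steps.** The plan has no figure of its own to reproduce on this point. The enrolment goal of at least 400 is not derived in the documents and is not affected. The check is a reading of the sequence.

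| Event | Ondansetron | Alcohol |
|---|---|---|
| Patient agrees, packet opened | Stated | Stated |
| Arm's checklist is inside the packet | Stated | Stated |
| Baseline score is step 1 of that checklist | Stated | Stated |
| Baseline card is inside the packet | Stated | Not stated |
| Any score requested before opening | None | None |
| Opening time recorded by a checklist step | None | None |

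Item 5 sets no nausea score for inclusion, so eligibility screening does not supply an earlier score either. For ondansetron, opening must come before the baseline. For alcohol it follows if the crew works from the enclosed checklist, but a crew could score first without breaking any written rule.

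**What a baseline shift would do.** All inputs here are assumed; none is in the documents. Define change as baseline minus later score. Let b be the between-arm difference in baseline shift caused by knowing the arm, and k the share of b that also appears in later scores (negative k means a later shift in the opposite direction).

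- Now: net bias = b − kb = b(1 − k).
- With the baseline taken before opening, if the later shift comes from knowing the arm: 0 − kb = −kb.
- With the baseline taken before opening, if the later shift was only anchoring on the earlier rating: 0.

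For b = 0.5 points:

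| k | Now, b(1 − k) | After, −kb |
|---|---|---|
| −0.5 | +0.75 | +0.25 |
| 0 | +0.50 | 0 |
| 0.25 | +0.375 | −0.125 |
| 0.5 | +0.25 | −0.25 |
| 0.75 | +0.125 | −0.375 |
| 1 | 0 | −0.50 |

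All entries scale with b, so b = 0.25 halves them. In the knowing-the-arm case the change lowers total bias when k² < (1 − k)², that is when k < 0.5. It leaves total bias unchanged at k = 0.5 and raises it above that.

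**Scale.** No equivalence margin is stated. Against an assumed margin of 1 point, b = 0.5 is 0.5/1 = 50%; against an assumed 2 points it is 0.5/2 = 25%.

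**The case against.** **Total bias may not fall.** Later scores are taken with the treatment known, and nothing in Item 6 describes blinding after opening. If they shift the same way as the baseline by more than half as much (k above 0.5), protecting the baseline alone enlarges the net bias: at b = 0.5 and k = 0.75 it goes from 0.125 to 0.375 in size. This stands as a limit on what can be claimed. It is not a reason to keep the present order, which does better in that case only because two unknown biases happen to cancel.

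**Post-treatment scores could be compared alone.** That drops the baseline from the formula, and the scores are already collected. But Item 2 asks about reduction, and if later ratings anchor on a shifted baseline, the post-treatment comparison still carries kb.

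**Times are already collected.** The Data Analysis Plan promises all relevant time intervals, but it does not name opening, and no checklist step records it. It is fair to say that with an enclosed card the order is fixed anyway, so an opening time adds little for ondansetron today. Its use is to confirm compliance once the order changes.

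**Concealment before opening is not absolute.** The plan commits to similar weight, shape and contour; matching for sound is only conditional. A score taken before opening is protected only as far as the packets hide their contents.

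**Stronger readings.** A reader might infer that the baseline is biased, that both checklists place the card in the packet, or that an error rate can be attached. The documents support none of these. They show an order of steps and no data on its effect; the enclosed card is explicit for ondansetron only; and they give no standard deviation, margin, significance level or allocation ratio from which an error rate could be computed.

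**Conclusion.** The point holds as an avoidable risk of bias. Followed as written, the plan places the baseline after the assignment can be known, explicitly for ondansetron and by inference for alcohol, and nothing requires an earlier score. Size and direction are unknown; the figures above rest on assumed b, k and margin and show only how a shift would carry through. The change should be made because it is standard practice and nearly free, although it is not shown to reduce this trial's total bias. It is secondary to the missing equivalence margin and the open-label later scores. Confidence is medium.

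**What to change.** 1. Attach the first score card and a pen to the outside of the sealed packet, beside the script.
2. Order the steps as consent, timed baseline score on the outside card, then opening. Write the opening time on the same card and require that the baseline time precede it.
3. Remove step 1 from both enclosed checklists.
4. Number the cards so that the first card in the present step 5 is the outside card and the third card in the present step 8 is the third overall, in both arms.
5. State in the protocol and the report that this protects the baseline only, that it depends on the packets concealing their contents, and that post-treatment scores remain open-label, so a lower total bias is not guaranteed.

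Cost: one card and a pen move outside, one step is reordered in two checklists, and one extra time is written down. No score, staff or visit is added. The downside is a small change to packet assembly and crew instructions.

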Item 4 Purpose and rationale Insert purpose, objectives and research questions/hypotheses here. If you cut and paste from another document, make sure the excerpted material answers the question	Insert purpose: IPA Therapy may offer a very inexpensive, easy to administer, and effective alternative to medication therapy for nausea and vomiting in the prehospital

Item 5 Study Population(s) Being Recruited  In your recruitment plan, how many different populations of prospective subjects do you plan to target? Provide number: 1	Identify the criteria for inclusion :	Identify the criteria for exclusion :
--	--	--

e.g., a population can be individuals with type 2 diabetes controlled with diet and/or a population of healthy controls. Or a population can be individuals attending an education program, etc.
 
List each different population on a separate row and provide a short descriptive label: (e.g., normal-healthy, diabetics, parents, children, etc.)
 
To add rows use copy & paste
		

EMS patients complaining of nausea
	
Adults (non-pregnant) age 18 years or older with a symptom of nausea and/or vomiting requiring treatment by EMS
	
 
• Children not yet 18 years of Age
 
• Prisoners or those under arrest
 
• Patients known or suspected to be Pregnant
 
• Clinical Intoxication
 
• Patients unable to provide informed consent
 
• Recent Upper respiratory Tract infection
 
• Inability to follow instructions
 
• Inability to inhale through Nares
 

#### Item 6

**Research Plan / Description of the Research Methods a.** *Provide a comprehensive narrative describing the research methods. Provide the plan for data analysis (include as applicable the sample size calculation).*

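### Changes in the 0-10 nausea score are compared by t-test with no baseline adjustment; ANCOVA on the baseline score already scheduled would generally narrow the confidence interval.

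*Combined protocol and SAP*

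**What the plan says.** Item 2 (abstract) sets the aim: "This will be a randomized equivalence study comparing the reduction in a" patient's reported nausea between ondansetron and isopropyl alcohol. Item 6, Data Analysis Plan, names the comparison: "Time to treatment will be compared between the two arms of the study as well as changes in Visual Nausea Severity Scores". It closes with: "T-test and confidence intervals will be utilized to determine statistical significance". No regression model, covariate or other adjustment is mentioned in any section.

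A baseline score is scheduled in both arms. Step 1 of the isopropyl alcohol checklist reads "Mark Time and Visual Nausea Severity Score 0-10"; step 1 of the ondansetron checklist reads "Mark Time and Visual Nausea Severity Score 0-10 on first enclosed card". On timing, the recruitment section of Item 6 says: "If the patient agrees to enroll then the study packet will be opened and utilized".

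On size, Item 6 says: "The goal is to enroll at least 400 patients over a 1 year period". No calculation supports that figure. The documents also give no SD, baseline to follow-up correlation, equivalence margin or allocation ratio.

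**The concern.** Subtracting baseline assumes that each extra point of nausea at baseline carries through as one extra point at follow-up. When the true slope differs from 1, baseline variation that could have been removed stays in the error term and widens the interval. Under randomization this causes no bias; the cost is precision.

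Precision matters here because an equivalence claim is decided by whether the confidence interval fits inside a margin. A needlessly wide interval makes true equivalence harder to show with the same patients. Leaving adjustment unspecified also allows a choice between adjusted and unadjusted results after the data are seen.

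**Working it through.** **Inputs from the documents.** Total of at least 400 patients; outcome is change in a 0-10 score; baseline is scored in both arms; method is the t-test. The 400 cannot be reproduced, because no alpha, power, SD, effect or margin is given.

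**Assumed inputs.** Equal allocation (200 per arm); correlation rho between baseline and follow-up of 0.3 to 0.6; k = follow-up SD / baseline SD of 0.75 to 1.5. Item 5 admits adults "with a symptom of nausea and/or vomiting requiring treatment by EMS" with no numerical cut-off, so the documents do not settle how widely baseline will spread relative to follow-up.

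**Formulas.** With baseline SD s_b, the per-patient variances that drive the treatment contrast are:

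- change score: s_b² × (1 + k² − 2·rho·k)
- ANCOVA: s_b² × k² × (1 − rho²)

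Their difference is s_b² × (1 − rho·k)². It is never negative and is zero only when the slope rho·k equals 1. Let R = ANCOVA variance / change-score variance. The change-score interval is then 1/√R times as wide, whatever the confidence level.

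*Example, k = 1, rho = 0.3:* change 1 + 1 − 0.6 = 1.40; ANCOVA 1 − 0.09 = 0.91; R = 0.91/1.40 = 0.650; 1/√0.650 = 1.240.

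| k | rho | R | Change-score interval wider by | ANCOVA patients for the same precision (400 × R) |
|---|---|---|---|---|
| 0.75 | 0.3 | 0.460 | 47.4% | 184 |
| 0.75 | 0.6 | 0.543 | 35.7% | 217 |
| 1 | 0.3 | 0.650 | 24.0% | 260 |
| 1 | 0.6 | 0.800 | 11.8% | 320 |
| 1.25 | 0.3 | 0.784 | 12.9% | 314 |
| 1.25 | 0.6 | 0.941 | 3.1% | 376 |
| 1.5 | 0.3 | 0.871 | 7.1% | 349 |
| 1.5 | 0.6 | 0.993 | 0.3% | 397 |

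**On the score scale.** Assume an SD of 2.5 at both times, rho = 0.5 and 200 per arm. The SD of change is 2.5 × √(2 × 0.5) = 2.5, so the 95% half-width is 1.96 × 2.5 × √(2/200) = 0.490 point. The ANCOVA residual SD is 2.5 × √0.75 = 2.165, giving 0.424 point.

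**Cost of estimating the slope.** The variance rises by a factor of about 1 + 1/(N − 4) = 1 + 1/396 = 1.0025, or 0.25%.

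**Simulation.** With 2,000 trials per setting and 200 per arm, the mean width ratios (change/ANCOVA) for rho 0.3 and 0.6 were 1.24 and 1.12 at k = 1, 1.47 and 1.35 at k = 0.75, and 1.07 and 1.00 at k = 1.5. Both estimators were unbiased.

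A second simulation used scores rounded and bounded to 0-10, with underlying SDs of 2.2 at baseline and 2.5 at follow-up. The ANCOVA standard error was 0.859, 0.918 and 0.970 times the change-score one for rho 0.3, 0.5 and 0.7, and it was smaller in at least 99.9% of runs. The formula at k = 2.5/2.2 = 1.136 gives 0.854, 0.916 and 0.970. The bounds and rounding therefore cost little; the smaller gain than at k = 1 comes from the SD ratio.

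**The case against.** **A valid analysis that already uses baseline.** True. The comparison here is against the change score, not against follow-up alone, and no error is claimed. What remains is a better method using data already scheduled.

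**The t-test is not tied explicitly to the nausea score.** Also true: the sentence closes a paragraph that covers several outcomes, so "unadjusted" is an inference. It is the only reading available, since no other method is named and a t-test takes no covariate.

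**The size is speculative and probably at the lower end.** This largely stands. Patients selected for nausea may be bunched at baseline while response varies at follow-up, which would favour k above 1 and gains of 13% down to almost nothing. The documents cannot settle it. Some combinations are also implausible in absolute terms: an SD of change of 3 with k = 0.75 and rho = 0.6 implies a baseline SD of 3/√0.6625 = 3.69, above the 3.16 of a uniform spread over 0 to 10. The ratios do not depend on this, but the k = 0.75 rows should be read as an outer bound.

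**Baseline may be marked after the arm is known.** This stands as a caution, because the first card is inside the packet. It affects both analyses. If knowing the arm shifts the recorded baseline by d in one arm, the change-score difference moves by the full d and the ANCOVA difference by about slope × d. The slopes in the grid run from 0.3 × 0.75 = 0.225 to 0.6 × 1.5 = 0.9. ANCOVA is then less exposed, but the two estimates no longer target exactly the same quantity.

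**Other gaps matter more.** Agreed. The margin is missing. The follow-up time differs between sections: 15 minutes or arrival in Item 2 and the Item 6 procedures, 10 minutes or arrival in step 6 of the ondansetron checklist. Rescue is possible after ten minutes in both arms, so a later score may follow it. These must be resolved for either analysis and do not remove the case for adjustment.

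**Conclusion.** The concern holds as an efficiency improvement that should be made, not as a validity error. The direction is secure: under randomization with roughly equal arms, ANCOVA estimates the same difference and is in large samples no less precise than the change score.

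The size is uncertain. The central illustration (equal SDs, rho 0.3 to 0.6) gives a change-score interval 24% to 12% wider, equivalent to needing 400 patients where 260 to 320 would do. Across the assumed grid the excess runs from 0.3% to 47%, and it is near zero when the slope is near 1. Equal allocation, rho and k are all assumptions. The effect on the equivalence conclusion cannot be stated without a margin.

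**What to change.** Add to the Data Analysis Plan in Item 6, once the time point has been reconciled and named:

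> The between-arm difference in nausea score at [named post-treatment time point] will be estimated by linear regression (ANCOVA) with treatment and baseline score as covariates. The adjusted difference and its confidence interval are the main result. The unadjusted comparison of change scores is supportive.

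Using change as the outcome in the same model gives an identical treatment estimate, so results can still be presented as reduction in nausea. The plan should also say how scores recorded after rescue are handled, since that defines the quantity being estimated.

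Preferably, have the baseline score marked before the packet is opened, so that it cannot be influenced by the assignment.

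The analysis change costs a few sentences and no new data. Moving the baseline score is a small operational change: attach the first card to the outside of the packet and edit step 1 of both checklists.

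### The t-test on time to treatment has no place for randomised patients still untreated at ED arrival, and so probably understates the ondansetron delay

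*Combined protocol and SAP*

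**What the plan says.** All of this is in Item 6 of the combined protocol and SAP.

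- **Randomisation comes before treatment.** After verbal permission: "If the patient agrees to enroll then the study packet will be opened and utilized". Opening the packet reveals the arm.
- **A time is available before treatment.** Step 1 of each checklist records the time with the baseline score; the ondansetron version reads "Mark Time and Visual Nausea Severity Score 0-10 on first enclosed card".
- **The treatment time comes after delivery.** Step 5 in both arms: "Record time of treatment on back of first Visual Nausea Severity Score card".
- **Delivery differs by arm.** The alcohol arm takes three nasal inhalations from a swab. The ondansetron arm starts an IV line if none is in place, and then: "If unable to obtain IV access in two attempts use intramuscular route".
- **Scores can be tied to ED arrival.** Ondansetron step 6: "Mark time and Second Visual Nausea Severity Score upon arrival to the Emergency Department or 10 minutes after treatment whichever comes first". Alcohol step 6: "Mark time and Subsequent Visual Nausea Severity Scores upon arrival to the Emergency Department at indicated time intervals". Step 8 in both arms asks for a score at ED arrival on the third card, with no condition on treatment.
- **Packets.** Step 11 returns the materials to the Medic Officer, and step 12 adds: "Used Study Packets will be collected by the Investigators".
- **Analysis.** "Time to treatment will be compared between the two arms of the study as well as changes in Visual Nausea Severity Scores". Intervals and scores are to be recorded for enrolled patients, and the methods are a t-test and confidence intervals. The plan gives no time origin for time to treatment, no analysis set, and no rule for a patient who was not treated.

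**The concern.** A t-test compares observed values. A randomised patient who reaches the ED before the dose, or declines once the arm is known, has no time to treatment. Neither checklist has a branch for such a patient. Following the plan therefore restricts this comparison to treated patients, although no exclusion is written down.

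The loss is unlikely to be balanced. Patients still waiting at ED arrival are those with long delays, and the arm that may need IV access should have more of them. Removing them lowers that arm's mean.

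Item 4 presents alcohol as an easy treatment to give. How often the comparator could not be delivered before arrival is evidence on that question. As the plan stands, the time-to-treatment comparison would neither count these patients nor report how many there were.

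**Working it through.** **No plan figure to reproduce.** The documents give no time to treatment, no transport time and no expected share untreated. The only size figure is the goal of at least 400 patients, with no derivation. Every time below is an assumption.

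**Direction.** Let T be time to treatment and A the time to ED arrival, both from step 1. A treatment time is recorded only if T < A, so the t-test estimates E[T | T < A] in place of E[T]. When A is unrelated to T, the first is never larger than the second. The gap grows as T becomes long relative to A.

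**Size, first model.** Ondansetron T is lognormal with log-SD 0.5, so its mean is the median × exp(0.5²/2) = median × 1.133. Arrival A is normal with SD 6 minutes and a floor of 5. Simulation gives:

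| Arrival mean (min) | Ondansetron median (min) | Mean of T, all patients (min) | Untreated at arrival | Understatement of mean (min) |
|---|---|---|---|---|
| 20 | 5 | 5.7 | 1.8% | 0.13 |
| 20 | 6 | 6.8 | 3.3% | 0.26 |
| 20 | 8 | 9.1 | 7.9% | 0.7 |
| 20 | 10 | 11.3 | 14.2% | 1.4 |
| 20 | 12 | 13.6 | 21.6% | 2.4 |
| 30 | 5 | 5.7 | under 0.1% | 0.01 |
| 30 | 8 | 9.1 | 0.9% | 0.17 |
| 30 | 10 | 11.3 | 2.5% | 0.47 |
| 30 | 12 | 13.6 | 5.1% | 0.96 |

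For alcohol (median 1.5 minutes, log-SD 0.4, arrival mean 20) the mean is 1.5 × exp(0.4²/2) = 1.6 minutes, and under 0.01% are untreated.

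**In patients.** If 400 split equally, each arm has 200 (the ratio is not stated). The worst row is 200 × 0.216 = 43 ondansetron patients without a value. The 8-minute row at 20-minute arrival is 200 × 0.079 = 16. With fast access and 30-minute arrival it is about none.

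**On the between-arm difference.** In the worst row the true difference is 13.6 − 1.6 = 12.0 minutes. The treated-only difference is (13.6 − 2.4) − 1.6 = 9.6 minutes. The direction is unchanged.

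**Second model, as a check.** Both T and A are lognormal. Alcohol has mean 2 (CV 0.5), ondansetron mean 6, 8 or 10 (CV 0.6), and arrival mean 15, 20 or 30 (CV 0.4). Ondansetron patients untreated at arrival run from 0.6% to 23.6%, and alcohol patients 0.04% or less. The between-arm difference is understated by 0.09 to 2.09 minutes (2% to 26%). In the middle case (ondansetron 8, arrival 20) 7.0% are untreated and the difference falls from 6.0 to 5.3 minutes (12%).

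**Scores.** Setting steps 6 and 8 side by side, a patient who is never treated can still have a baseline score and an ED-arrival score, and hence a score change. Only a score timed a set number of minutes after treatment needs a treatment time.

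**The case against.** **The plan excludes no one.** It records data for enrolled patients, and enrolment precedes treatment. This stands as a statement about recording. It cannot supply a treatment time for a patient who was not treated, and the t-test then leaves that patient out.

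**The number may be small.** An IV line may already be in place, the IM route limits failed access, and crews may treat before departure. This stands: with fast access or long transport the bias is negligible. The IM route follows two failed attempts, though, so it does not prevent delay. Refusal once the arm is known could occur in either arm, so only the access delay supports expecting an imbalance.

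**It matters little to the conclusion.** The design statement concerns reduction in nausea, and the bias works against alcohol, so it cannot create a false speed advantage. Paramedics also rate ease and time needed. All of this stands, and it limits the weight of the point.

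**Stronger readings a reader might infer.** Three are tempting, and the documents support none of them:

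- *Scores exist only for treated patients.* Ondansetron step 6 allows ED arrival as the trigger, and step 8 in both arms requires an ED-arrival score whether or not treatment was given.
- *Opened but undelivered packets vanish with their patients.* Packets are numbered, step 11 returns them and step 9 documents interventions in the electronic record, from which data are also abstracted. A used packet plausibly means an opened one. No reconciliation rule is written, but a lost packet need not be a lost patient.
- *Randomisation no longer protects the score contrast.* That would require untreated patients to lack ED-arrival scores, which the checklists do not imply.

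**Conclusion.** The point holds for the time-to-treatment comparison. The treatment time is written only after delivery and the only stated methods are a t-test and confidence intervals, so a randomised patient untreated at ED arrival contributes nothing. The ondansetron arm probably loses more long delays, which would understate its delay.

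The size depends wholly on assumed access and transport times. It ranges from near 0% untreated and negligible bias to about 22% untreated and 2.4 minutes with slow access and 20-minute transport. The second model gives a similar range. Both models treat arrival as unrelated to time to treatment, which fails if crews wait on scene to give the drug. The bias runs against alcohol and did not reverse the direction in any case tried.

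The fix is worth making because it is cheap and uses a time already collected. This is not a threat to the nausea comparison.

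**What to change.** 1. **Time origin.** Define time to treatment as running from the time marked at step 1.
2. **Analysis set.** Count every opened packet in its assigned arm.
3. **Method.** In place of a t-test on treated patients only, keep untreated patients as not treated by ED arrival. Use either a Kaplan-Meier curve censored at ED arrival or the proportion treated by a prespecified time. The curve assumes that arrival is unrelated to the time treatment would have been given. The proportion avoids this if anyone arriving untreated counts as not treated, but the time point must be fixed in advance.
4. **Checklist line, both arms.** If treatment is not given or not completed, record the reason and time, and still complete the ED-arrival score.
5. **Packets.** Reconcile all opened numbered packets, and state that an opened packet counts as used.
6. **Reporting.** Give the number untreated at ED arrival by arm.

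While editing, reconcile the score timing: the methods text says 15 minutes after treatment, ondansetron step 6 says 10, and alcohol step 6 refers to intervals that are not specified.

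The cost is one checklist line, a packet tally by the Medic Officer who already receives the packets, and a few sentences in the analysis plan. The downside is slightly more form work.
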